This PhD study will contribute with new knowledge on the association between different types of BPD and psychiatric comorbidity. As BPD affects a large part of the population, this is a very important area of research from a public health and clinical perspective. Access to nationwide registries facilitates a comprehensive and population-based dataset, ensuring the ideal circumstances for investigating the association between BPD and potential psychiatric comorbidity. Furthermore, the results can be used to increase clinical awareness of vulnerable patients in the intersection between rheumatology and psychiatry and subsequently improve prevention and clinical management for a complex and resource-demanding patient population.

Materials and methods

Setting and study population

This PhD project includes a population-based nationwide cohort based on data from Danish health registries. Danish health registries, including The Danish National Patient Registry (DNPR), a subdivision of the DNPR, the National Patient Registry – Psychiatry (NPD-Psych), The Danish National Prescription Database and The Danish National Health Service Register, contains complete data on hospital contacts, prescription drug use and services provided by health contractors. By using the Danish Civil Registry and the unique personal identification number assigned to all Danish citizens at birth, data across registries can be linked on an individual level^{34 35 36 37}.

The study population will be defined as all adult patients (18+) identified in the DNPR³⁴, covering all inpatient and outpatient services in Denmark, in the time period 1th of January 2010 to 31th of December 2014 with a diagnosis of BPD according to the ICD-10 Classification of Disease (DM*).³⁰

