Psychiatric comorbidity will be defined as the presence of any of the following diagnosis, according to ICD-10 classification³⁰, obtained from the National Patient Registry – Psychiatry (NPD-Psych), covering all inpatient and outpatient psychiatric services in Denmark in the time period 1th January 2007 to 31th December 2017: Organic, including symptomatic, mental disorders (F00-DF09), Mental and behavioral disorders due to psychoactive substance use (F10-F19), Schizophrenia, schizotypal and delusional disorders (F20-F29), Mood [affective] disorders (F30-F39), Neurotic, stress-related and somatoform disorders (F40-F48), Behavioral syndromes associated with physiological disturbances and physical factors (F50-F59), Disorders of adult personality and behavior (F60-F69), Mental retardation (F70-F79), Disorders of psychological development (F80-F89), Behavioral and emotional disorders with onset usually occurring in childhood and adolescence (F90-F98) and, Unspecified mental disorder (F99). To qualify as a psychiatric comorbidity to back pain disorder, we define that the psychiatric diagnosis must be given no earlier than three years prior to back pain disorder diagnosis and no later than three years after.

Study 1) Prevalence of psychiatric comorbidity in back pain disorders

Psychiatric comorbidity in Back Pain Disorders
Risk, treatment and pharmaco-epidemiological analysis

Aim: 1) To estimate prevalence of psychiatric comorbidity in patients with BPD compared to patients without BPD and 2) To estimate prevalence of psychiatric comorbidity in patients with unspecific back pain (UBP) compared to the background population and to patients with a specific back pain (SBP) in a Danish nationwide cohort from 2010-2014.

Hypothesis: 1) There is a higher risk of psychiatric comorbidity in BPD patients compared to the background population and 2) UBP patients have a higher risk of psychiatric comorbidity compared to patients with specific BPD.

Design: The study will be a nationwide register-based matched cohort study.

Procedure: Selected BPD patients with the following diagnosis will be identified via the DNPR: Spondylopathies DM45-49, Other dorsopathies DM 50-54 and Segmental and somatic dysfunction DM99. Each patient will be matched 1:5 on age and sex with patients without back disorders by random at Statistics Denmark³⁸. The selection of diagnosis is to be able to match the population with non-BPD patients in the Danish registries.

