Information on somatic comorbidity for calculation of Charlson Comorbidity index³⁹ (CCI) at time of BPD diagnosis, will be retrieved from the DNPR. Data on psychiatric comorbidity will be identified using NPD-Psych. Information on marital status, vital status, and immigration status will be retrieved from the Civil Registration System (CPR)³⁵. Patients that are not alive or have emigrated within three years after BPD diagnosis are considered lost to follow-up and excluded from the cohort. Descriptive data on the socioeconomic status, education level and equivalent available income will be retrieved from Statistics Denmark³⁸. All data comprising each variable will be retrieved from 1th of January 2007 to 31th of December 2017 (three years before and after study period).

Measures of outcome: Primary outcome is to estimate prevalence of psychiatric comorbidity in patients with BPD compared to the Danish background population. Secondary outcome is to estimate prevalence of psychiatric comorbidity stratified by type of BPD (SBP UBP) compared to the Danish background population. We will use a presence of psychiatric comorbidity as outcome.

Statistics: We will use Fisher's exact test and t-test to compare baseline characteristics with 95% confidence intervals (CI) and p-values. Crude risks of psychiatric comorbidity will be calculated and logistic regression model will be used, to investigate differences between the distribution of risk in BPD patients and the background population. A logistic regression model will also be used to investigate differences between the distribution of psychiatric comorbidity in the IBD, DBD and UBP group compared to the background population. The logistic regressions will be reported using 95% CI and adjusted for the following confounders: age, sex, equivalent available income, educational level, CCI, marital status.

Study 2) The effect of psychiatric comorbidity on type of treatment for BPD

Aim: 1) To investigate whether treatment of BPD in patients with psychiatric comorbidity differ from treatment of patients with BPD without psychiatric comorbidity; 2) To investigate whether treatment of BPD differs in the following subgroups: a) specific BPD and no psychiatric comorbidity; b) specific BPD with psychiatric comorbidity; c) unspecific BPD with no psychiatric comorbidity; d) unspecific BPD with psychiatric comorbidity. Investigation will be performed in a nationwide Danish cohort in 2010-2014.

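### Study 1 compares BPD patients who all have a hospital contact with population controls who need none, so part of any excess in psychiatric diagnoses may reflect hospital use rather than back pain disorder

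*Combined protocol and SAP*

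**What the plan says.** **Entry of BPD patients.** Under Setting and study population, patients come from the Danish National Patient Registry (DNPR), described as "covering all inpatient and outpatient services in Denmark". Study 1, Procedure, repeats the source: "Selected BPD patients with the following diagnosis will be identified via the DNPR".

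**Controls.** Study 1, Procedure: "Each patient will be matched 1:5 on age and sex with patients without back disorders by random at Statistics Denmark". The next sentence adds "The selection of diagnosis is to be able to match the population with non-BPD patients in the Danish registries". No contact criterion and no index date are given for controls. Measures of outcome then names the comparator: "Primary outcome is to estimate prevalence of psychiatric comorbidity in patients with BPD compared to the Danish background population".

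**Outcome.** Psychiatric comorbidity is a diagnosis in the psychiatric register, "covering all inpatient and outpatient psychiatric services in Denmark in the time period 1th January 2007 to 31th December 2017". The plan describes this register as part of the DNPR. A diagnosis counts from three years before to three years after the BPD diagnosis.

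**Adjustment.** Study 1, Statistics, lists marital status, education, income, the Charlson index (CCI), age and sex. It contains no measure of hospital or other health-care use, and no sensitivity analysis on this point is planned.

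**The concern.** Being counted as exposed and being counted as a psychiatric case both require specialist care. Being a control does not. Two mechanisms could therefore raise the recorded psychiatric prevalence in the BPD group without any role for back pain disorder itself:

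- **Referral.** A hospital contact may lead to psychiatric referral and coding. This can act only on diagnoses made after the index contact.
- **Care-seeking.** People who use hospital care may differ from the general population in how readily they seek care and are diagnosed. This can act over the whole six-year window.

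What is at stake is the interpretation. The thesis aim frames the comparator as people free of back pain, the section on clinical contributions promises knowledge about an association, and the model adjusts for listed confounders. Together these invite the reader to take the estimate as an association of back pain disorder with psychiatric illness. The planned contrast cannot separate that from an excess that any group of hospital patients might show against the population. A large cohort does not help: it narrows the interval around the same mixture.

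**Working it through.** The documents state no prevalence, effect size, sample size or power for Study 1, so there is no figure of the plan to reproduce. What follows illustrates the size under stated assumptions.

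**Inputs**
- From the plan: all BPD patients have a hospital contact, and controls have none required of them.
- Assumed: hospital contact multiplies the risk of a recorded psychiatric diagnosis by f = 1.2 to 1.5.
- Assumed: a share h = 0.3 to 0.7 of controls also have hospital contact.
- Assumed for the illustration: no association between BPD and psychiatric diagnosis once contact is taken into account, and no absorption of the effect by the adjustment variables.

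**Formula.** Let p0 be the risk without contact.
- BPD patients: f·p0.
- Controls: h·f·p0 + (1 − h)·p0 = p0·(1 + h(f − 1)).
- Spurious ratio: f / (1 + h(f − 1)).

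The last two columns divide an illustrative observed ratio by the spurious one.

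| f | h | Spurious ratio | Observed 2.0 becomes | Observed 1.5 becomes |
|---|---|---|---|---|
| 1.2 | 0.3 | 1.2/1.06 = 1.13 | 1.77 | 1.33 |
| 1.2 | 0.7 | 1.2/1.14 = 1.05 | 1.90 | 1.43 |
| 1.5 | 0.3 | 1.5/1.15 = 1.30 | 1.53 | 1.15 |
| 1.5 | 0.7 | 1.5/1.35 = 1.11 | 1.80 | 1.35 |

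If every control also had contact (h = 1), the spurious ratio would be f/f = 1.00. This is why a comparison with hospital-contact controls is informative.

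**Odds-ratio scale.** The plan uses logistic regression. With p0 = 2% or 4% (assumption) and the same h, f = 1.5 gives spurious odds ratios of 1.11 to 1.32, so the scale matters little here. The choice of f matters much more: f = 2 gives 1.18 to 1.59, and f = 3 gives 1.27 to 1.99.

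**Which comparisons are affected.** The primary model and the models setting inflammatory, degenerative and unspecific BPD each against the background population share the asymmetry. The contrast of unspecific with specific BPD in Hypothesis 2 is much less affected, because both groups enter through the DNPR.

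**The case against.** The strongest reply is that Hypothesis 1 and the primary outcome are worded as a contrast with the background population. For that question a random sample matched on age and sex is the right comparator, and hospital-contact controls answer a different question. This stands. It is the reason to leave the primary analysis unchanged and to treat the point as one of interpretation plus a supplementary analysis.

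Other parts of the reply also carry weight:

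- **Sampling frame.** The words about non-BPD patients in the registries could mean that controls have some registry contact. The population reading is better supported, because the hypothesis, the primary outcome and the statistics paragraph all name the background population. Still, the documents do not settle it. A reader might infer that controls have no hospital contact at all; the documents say only that none is required.
- **Size.** A reader might divide the observed ratio by the full contact factor and conclude that an observed 1.5 could disappear (1.5/1.5 = 1.00). That holds only if no control has hospital contact, which nothing in the documents supports. With 30 to 70% contact and a factor of up to 1.5, the result does not fall below 1.15.
- **Timing.** The index contact cannot cause psychiatric diagnoses made in the three years before it, so referral explains at most the post-index part.
- **Partial cover.** CCI is built from DNPR diagnoses and may absorb some of the difference. It measures selected somatic diseases, however, not contact, and in controls it can be recorded only if they had a contact. The Introduction concedes that the missing primary care data leave only severe psychiatric diagnoses. It does not say that capture may differ between the groups.

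**Conclusion.** The asymmetry is real and nothing planned examines it. The primary contrast remains valid as a description of hospital-diagnosed BPD patients against the population; the documents do not support calling it invalid. They also do not show how much of an excess is due to hospital use. Under the assumed factor of 1.2 to 1.5 and 30 to 70% contact among controls, the spurious ratio is about 1.05 to 1.30, enough to weaken a moderate association but not to remove an observed 1.5. The figure rests wholly on those two assumptions and ignores whatever CCI and the other covariates absorb; a larger contact factor would give a larger distortion. One supplementary analysis and more exact wording of the result should be added.

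**What to change.** 1. Keep the primary analysis, and describe its result as hospital-diagnosed BPD against the background population.
2. State the sampling frame for controls, including whether any registry contact is required, and give each control the index date of its matched patient. The outcome window and CCI are both defined from the BPD diagnosis, which controls do not have.
3. Pre-specify one sensitivity analysis: repeat the primary model with controls restricted to those with a somatic DNPR contact for a non-back diagnosis in the index year. Retain adjustment for age and sex, because the restriction breaks the 1:5 sets.
4. In that analysis, report psychiatric diagnoses before and after the index date separately, since referral can act only on the latter.
5. Present the result beside the primary estimate as a conservative comparison. It should not be called a guaranteed lower bound: selecting controls by hospital contact may over-represent psychiatric illness, and one contact in a year does not equalise intensity of use. Nor should it serve as an all-or-nothing rule for attributing the excess to BPD, because an estimate that may overcorrect can vanish while an association exists.

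**Cost.** A little extra data handling and analysis. DNPR records for controls are already needed for CCI, but the plan does not say that all their somatic contacts will be extracted, so the data request should be checked. Restricted controls will be sicker than average, so the estimate may overcorrect.

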Measures of outcome: The outcome is type of treatment for BPD (surgical, pharmacological and other types of treatment)

Statistics: We will use Fisher's exact test and t-test to compare patients' baseline characteristics with 95% confidence intervals (CI) and p-values. For each treatment type we will use logistic regression model to investigate differences in outcome distribution between patients with and without psychiatric comorbidity. The logistic regressions will be performed with 95% CI adjusted for the following confounders: age, sex, CCI, level of education, equivalent available income, type of BPD (IBD, DBD or UBP) and marital status.

Study 3) Effect of psychiatric comorbidity in pharmacological treatment of BPD.

Aim: 1) To compare dosages of pharmacological treatment in BPD patients with and without the presence of psychiatric comorbidity in a nationwide Danish cohort study in 2010-2014. 2) To compare high vs. low dosages of pharmacological treatment for BPD in patients with BPD and psychiatric comorbidity.

Hypothesis: 1) Patients with BPD and psychiatric comorbidity are prescribed a higher dosage of pain medication for BPD compared with BPD patients without psychiatric comorbidity. 2) BPD patients with a psychiatric comorbidity with a high (defined as above the 50th percentile) vs. low (defined as below the 50th percentile) dosage of pain medication are also prescribed higher dosages of psychiatric medication.

Design and study population: The study will be a nationwide register-based cohort study. The study population consists of patients with BPD that received pharmacological treatment for BPD. In the secondary analysis the study population consists of patients with BPD and a psychiatric comorbidity, who received pharmacological treatment for BPD.

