Statistics: We will use Fisher's exact test and t-test to compare patients' baseline characteristics with 95% confidence intervals (CI) and p-values. Time dependent Cox regression will be performed separately for patients with specific and unspecific BPD to examine dosage of pharmacological treatment over time comparing patients with and without psychiatric comorbidity. The analysis will be performed with 95% CI and adjusted for the following confounders: age, sex, CCI, level of education, equivalent available income, marital status and the presence of psychopharmacological treatment.

To examine dosage of psychopharmacological treatment over time comparing patients with psychiatric comorbidity and low vs high dose of pharmacological treatment of BPD, time dependent Cox regression will be performed reporting 95% CI and adjusting for the following confounders: age, sex, CCI, level of education, equivalent available income, marital status.

Psychiatric comorbidity in Back Pain Disorders
Risk, treatment and pharmaco-epidemiological analysis

Ethics

All studies will be based on national clinical registries and approval is obtained by The Danish Health Data Board and the Danish Data Protection Agency (18/3337). According to Danish law, further ethical approval is not required for purely registry-based studies. All data will be stored on Statistics Denmark's servers and will be anonymized ensuring no patients can be identified.

PhD Outline

The PhD will be conducted within a timeframe of three years (six semesters).

	1st semester	2nd semester	3rd semester	4th semester	5th semester	6th semester
Data collection	X					
PhD Courses	X	X	X			
Data analysis		X	X	X	X	
Writing articles			X	X	X	X

References

1. Hawker GA. The assessment of musculoskeletal pain. *Clinical and experimental rheumatology* 2017;35 Suppl 107(5):8-12.

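### Year of BPD diagnosis (Studies 2 and 3) and immigrant origin, if the retrieved item holds it (Studies 1 to 3), are in none of the four adjustment sets, which leaves plausible confounding unadjusted

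*Combined protocol and SAP*

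**What the plan says.** The Procedure paragraphs of Studies 1, 2 and 3 each contain the sentence "Information on marital status, vital status, and immigration status will be retrieved from the Civil Registration System (CPR"). Marital status then appears in every covariate list. Vital status and emigration are used in the sentence that follows: "Patients that are not alive or have emigrated within three years after BPD diagnosis are considered lost to follow-up and excluded from the cohort". No purpose is stated for immigration status.

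The four adjustment sets, in the Statistics paragraphs, are:

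- Study 1: "adjusted for the following confounders: age, sex, equivalent available income, educational level, CCI, marital status"
- Study 2: "adjusted for the following confounders: age, sex, CCI, level of education, equivalent available income, type of BPD (IBD, DBD or UBP) and marital status"
- Main comparison of Study 3: "adjusted for the following confounders: age, sex, CCI, level of education, equivalent available income, marital status and the presence of psychopharmacological treatment"
- Secondary comparison of Study 3: "adjusting for the following confounders: age, sex, CCI, level of education, equivalent available income, marital status"

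Entry runs from 2010 to 2014 (Setting and study population). Treatment is followed for three years after diagnosis, so to 2017 at the latest. For Study 1, "Each patient will be matched 1:5 on age and sex with patients without back disorders by random at Statistics Denmark". No index date is defined for these comparators.

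**The concern.** The plan presents its covariates as confounders, so the lists are meant to be the full set of measured variables to control. Two candidates are missing.

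**Origin.** Both the back pain and the psychiatric diagnoses come from hospital registers, and the Introduction acknowledges that primary-care data are incomplete. Origin could plausibly influence who reaches hospital care for either condition, and who receives surgery, psychological treatment or opioids. If so, it would be associated with exposure and outcome in each study.

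**Calendar year.** Entry covers five years. If prescribing and psychiatric coding both shifted over that time, diagnosis year would link psychiatric comorbidity to treatment in Study 2 and to dose in Study 3. The secondary comparison of Study 3 is open to the same problem. Its exposure groups are split at the 50th percentile of pain-medication dose, with no mention of a cut by year, so diagnosis year could partly decide who counts as high dose.

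At stake is a modest bias in adjusted odds ratios (Studies 1 and 2) and hazard ratios (Study 3). A large sample does not shrink it.

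**Working it through.** **Step 1: item check.** The plan gives no sample size, power or effect size, so there is no figure to reproduce. Reading the four lists item by item:

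| Set | Covariates | Immigration status or origin | Diagnosis year |
|---|---|---|---|
| Study 1 | 6 | no | no |
| Study 2 | 7 | no | no |
| Study 3, main | 7 | no | no |
| Study 3, secondary | 6 | no | no |

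Each variable is in 0 of 4 sets.

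**Step 2: origin, illustration.** All inputs are assumptions. Let p1 and p0 be the immigrant shares in the exposed and unexposed groups, and RR the risk ratio of the outcome by origin. The bias factor for a risk ratio is [1 + p1(RR − 1)] / [1 + p0(RR − 1)].

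- Equal shares (10% and 10%), any RR: 1.00
- 15% vs 10%, RR 1.3: 1.045/1.03 = 1.015
- 15% vs 10%, RR 2: 1.15/1.10 = 1.045
- 20% vs 10%, RR 1.8: 1.16/1.08 = 1.074
- 20% vs 10%, RR 3: 1.40/1.20 = 1.167

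**Step 3: calendar time in Studies 2 and 3, illustration.** All inputs except the five-year span are assumptions. Take equal numbers in each of five entry years, y = 0 to 4. Psychiatric comorbidity starts at 10% and rises by a relative g1 per year. Outcome risk starts at 20% and rises by a relative g2 per year. Comorbidity has no true effect. The bias factor is the mean outcome risk weighted by the exposed, divided by the mean weighted by the unexposed.

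Worked case, g1 = 10% and g2 = 20%:

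- Exposed shares: 0.100, 0.110, 0.121, 0.133, 0.146 (sum 0.6105)
- Outcome risks: 0.200, 0.240, 0.288, 0.346, 0.415
- Exposed mean: 0.1880/0.6105 = 0.308
- Unexposed mean: 1.3004/4.3895 = 0.296
- Ratio: 1.039

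Other cases: g1 = g2 = 5% gives 1.005; g1 = 0 gives 1.00 for any g2. A trend in the outcome alone does not confound.

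**Step 4: calendar time in Study 1.** If each comparator takes the matched patient's index date, every year holds cases and comparators in the ratio 1:5. The year weights are then the same in both groups, and the factor is 1.00 however uneven the yearly counts. The plan does not say that comparators receive such a date.

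**Step 5: can these factors be compared with sampling error?** Only with further assumptions. Assume 10% prevalence in both groups and 1:5 matching. The variance of a crude log odds ratio with n BPD patients is then (1/0.09)(1 + 1/5)/n = 13.33/n. For the 95% half-width to equal ln(1.045/1.03) = 0.01446, n = 13.33 × (1.96/0.01446)² ≈ 245,000. At 5% prevalence the figure is about 460,000. The documents give neither n nor prevalence.

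**The case against.** Several points on the other side are sound and limit the claim.

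- A reader might infer that diagnosis year is known for everyone. It is known for BPD patients. Study 1 comparators have no back disorder and so no diagnosis date. The gap there is the undefined index date, and inheriting the matched patient's date closes it by design.
- A reader might infer that origin is collected and then ignored. The item sits beside vital status and directly before the emigration exclusion, so it may mean migration data for follow-up. The text does not settle this, and the availability of origin is therefore conditional.
- A reader might infer that confounding has been shown. It has not. Each variable must relate to both exposure and outcome after adjustment for income, education, CCI and marital status, which may absorb part of any effect of origin. The bias factors above treat the whole assumed imbalance as residual. For calendar time, the span is only five years, and every patient has the same three-year windows, fully covered by 2007-2017 data.
- A reader might infer that the bias exceeds sampling error because the cohort is nationwide. Without a sample size or prevalence, this cannot be said.
- It is also tempting to argue that diagnosis year is safe to adjust for because it is fixed before exposure and outcome. Psychiatric diagnoses count from three years before the back pain diagnosis, so that ordering does not hold. The case for including year rests on secular trends.

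What remains against the point is that the choice of covariates is a judgement. The plan, however, gives no reason for leaving these out, and diagnosis year is already in hand.

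**Conclusion.** The point holds as a minor, nearly free improvement. That neither variable is in any of the four adjustment sets is certain from the text. That this leaves confounding is plausible only: by calendar time in Studies 2 and 3, and by origin in Studies 1 to 3. Under the assumed inputs, calendar time gives 1.00 to 1.04. Origin gives 1.00 to roughly 1.07 under moderate assumptions, and up to 1.17 only with a doubled immigrant share and a threefold risk. Both ranges include no bias. The factors are for risk ratios and carry over only approximately to the odds ratios of Studies 1 and 2 and the hazard ratios of Study 3. The documents contain nothing that would narrow these ranges or set them against sampling error.

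**What to change.** Before analysis, make four changes to the plan.

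1. Add calendar year of BPD diagnosis as a categorical covariate (five years, so four indicator terms) to each logistic model in Study 2 and to both Cox models in Study 3.
2. State whether immigration status means origin or migration dates used for follow-up.
3. If origin is available, add it as a categorical covariate in the models of Studies 1, 2 and 3.
4. In Study 1, give each comparator the index date of the matched BPD patient.

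The cost is a few lines of text. Diagnosis year needs no new data. Origin needs none if the retrieved item already holds it; if only migration dates are retrieved, it would need a further variable.

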Hypothesis: 1) Psychiatric comorbidity affects type of treatment in BPD patients and 2) psychiatric comorbidity affects type of treatment in subgroups of BPD.

Design and study population: The study will be a nationwide register-based cohort study. The study population consists of patients with BPD and in the sub-analysis the study population consists of patients with BPD and psychiatric comorbidity.

Procedure: BPD patients will be identified via the DNPR. Surgical treatment will be defined as the presence of any procedure code for back surgery retrieved from DNPR (NOMESCO: KNA-W)³⁴⁻⁴⁰. Pharmacological treatment of BPD will be defined as any treatment with the following drugs: NSAID (ATC: N01A*), acitomenophen (ATC: N02BE01), opioids (N02A*), antiepileptica (ATC: N03A) and tricyclic antidepressants (ATC: N06AA)¹³ identified using the Register of Medicinal Products Statistics⁷. Data on other types of treatment (defined as any treatment not surgical or pharmacological) such as physiotherapist, psychologist, chiropractor or occupational therapist (covered via tax-funded health insurance) will be obtained via The Danish National Health Insurance Service Register (SSR)³⁷. All BPD treatment-related information will be retrieved up to three years after the date of BPD diagnosis.

Information on somatic comorbidity for calculation of Charlson Comorbidity index³⁹ (CCI) at time of BPD diagnosis, will be retrieved from the DNPR. Data on psychiatric comorbidity will be identified using NPD-Psych. Information on psychiatric comorbidity will be used to define whether each patient had a psychiatric diagnosis prior to BPD diagnosis, after BPD diagnosis or no psychiatric diagnosis. If a psychiatric diagnosis occurs both prior to and after BPD diagnosis, the patient will be defined as having a psychiatric comorbidity prior to BPD diagnosis.

Information on marital status, vital status, and immigration status will be retrieved from the Civil Registration System (CPR)³⁵. Patients that are not alive or have emigrated within three years after BPD diagnosis are considered lost to follow-up and excluded from the cohort. Descriptive data on the socioeconomic status, education level and equivalent available income will be retrieved from Statistics Denmark³⁸. All data comprising each variable will be retrieved from 1th of January 2007 to 31th of December 2017 (three years before and after study period).

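### Residence in Denmark is required for the three years after BPD diagnosis but not the three years before, so recent arrivals have an incompletely observed psychiatric look-back

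*Combined protocol and SAP*

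**What the plan says.** The window for psychiatric comorbidity is set in the combined protocol and SAP under *Setting and study population*: "the psychiatric diagnosis must be given no earlier than three years prior to back pain disorder diagnosis and no later than three years after". The source is the psychiatric part of the national patient registry, described as "covering all inpatient and outpatient psychiatric services in Denmark in the time period 1th January 2007 to 31th December 2017".

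Eligibility under the same heading is by age, registry contact and a BPD diagnosis in 2010–2014: "The study population will be defined as all adult patients (18+) identified in the DNPR". The Procedure text of Studies 1, 2 and 3 then adds the same exclusion each time: "Patients that are not alive or have emigrated within three years after BPD diagnosis are considered lost to follow-up and excluded from the cohort". That rule looks forward only.

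Immigration status is retrieved from the civil registration system in all three studies. No eligibility rule, matching factor or model covariate uses it. Study 1 matches controls 1:5 on age and sex. Its model adjusts for age, sex, income, education, Charlson index (CCI) and marital status.

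Study 2 also uses the psychiatric data to "define whether each patient had a psychiatric diagnosis prior to BPD diagnosis, after BPD diagnosis or no psychiatric diagnosis". A diagnosis on both sides of the BPD date counts as prior. There is no category for an incomplete look-back.

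**The concern.** The plan treats leaving Denmark after the BPD diagnosis as loss of observation and excludes those patients. It does not treat time spent outside Denmark before the diagnosis in the same way, although half of the comorbidity window lies there. Someone who arrived one year before the index date has one of three look-back years on record and is analysed as fully observed.

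Missing information is therefore read as absence of disease. In Study 1 this lowers estimated prevalence. It also shifts the comparison with controls if recent arrivals are more common in one group, which matching on age and sex and the listed covariates do not prevent. In Studies 2 and 3 some exposed patients enter the unexposed group. In Study 2 the order of psychiatric and back pain diagnoses can also be recorded wrongly.

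**Working it through.** **Does anything else in the plan close the gap?** Data are extracted for 2007–2017, so every index date in 2010–2014 has three calendar years of register coverage before it. That is a data window; it cannot supply records for time spent abroad. The register limitation named in the Introduction is incomplete primary-care data, which is a different matter. The gap stays open.

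**Who is affected?** Only people who immigrated or returned within three years before index, and only for the time before arrival.
- A Danish diagnosis made between arrival and index is still captured as prior.
- A person with no psychiatric history is coded correctly.
- A person whose only in-window diagnosis was abroad is coded as having none, in all three studies.
- In Study 2, a person with a prior diagnosis abroad and a new Danish diagnosis after index is labelled *after*. The rule that both sides count as prior cannot operate on a diagnosis the register does not hold.

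**Size.** The documents state no prevalence and no share of recent arrivals, so there is no figure of the plan's own to reproduce. Every input below is assumed:
- f = share of the group that arrived within three years before index: 1–5%.
- m = mean fraction of the look-back missed. With arrival spread evenly over the three years, m = 1.5/3 = 0.5.
- w = share of cases whose only in-window diagnosis lies in the look-back: 0.3–0.5. The value 0.5 corresponds to one diagnosis per case, spread evenly over six years (3/6).
- Recent arrivals have the same true psychiatric rate as everyone else.

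Observed prevalence = p × (1 − f × m × w), so the relative loss is f × m × w:
- lowest: 0.01 × 0.5 × 0.3 = 0.15%
- highest: 0.05 × 0.5 × 0.5 = 1.25%

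For the prevalence ratio, p cancels and the bias factor is (1 − f₁mw)/(1 − f₀mw), with f₁ for patients and f₀ for controls:
- equal shares: exactly 1
- 1% of patients, 4% of controls, w = 0.5: 0.9975/0.9900 = 1.0076
- 1% of patients, 4% of controls, w = 0.3: 0.9985/0.9940 = 1.0045

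The ratio is therefore inflated by about 0.5–0.8%. Reversing the shares gives 0.9900/0.9975 = 0.992 and 0.9940/0.9985 = 0.995, a deflation of similar size.

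On the odds-ratio scale that Study 1 uses, assume true prevalences of 10% and 6%. The true OR is (0.10/0.90)/(0.06/0.94) = 1.741.

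| Share in patients / controls | OR, m = 0.5, w = 0.3 to 0.5 |
|---|---|
| 1% / 1% | 1.741 to 1.741 |
| 5% / 5% | 1.740 to 1.740 |
| 2% / 5% | 1.749 to 1.754 |
| 5% / 2% | 1.732 to 1.726 |
| 2% / 10% | 1.763 to 1.778 |
| 10% / 2% | 1.717 to 1.702 |

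If the whole look-back were missed (m = 1.0), the last two rows become 1.786 to 1.818 and 1.694 to 1.662.

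**Study 2 labels.** Assume each truly *prior* patient has one prior diagnosis, spread evenly over the look-back. The share whose prior diagnosis is unseen is then f × m, or 0.5% at f = 1% and 2.5% at f = 5%. These patients are recorded as *after* or *none*, depending on whether a Danish diagnosis follows.

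**The case against.** The strongest reply is that the plan defines comorbidity by a Danish register, says that register limitations must be weighed in interpretation, and does not claim to capture all psychiatric disease. On that view, care abroad is simply outside the measure. This stands in part. But the plan itself excludes emigrants as unobserved, and the same reasoning applies before index; its stated limitations do not mention migration.

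A second reply is that excluding recent arrivals narrows a nationwide cohort to remove a small bias. This is fair, and it is why a sensitivity analysis is an acceptable alternative.

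Four stronger readings are tempting, and the documents do not support them.
- *Recent immigrants have no look-back at all.* Only the time before arrival is missing.
- *The prior/after mislabelling biases Study 2's treatment comparison.* The stated regression contrasts comorbidity present with comorbidity absent, and diagnoses on either side of index qualify. A patient moved from *prior* to *after* remains exposed. Only those whose sole in-window diagnosis was abroad change group.
- *Study 3 mislabels prior disease as new.* Study 3 has no prior/after split; it can only place an exposed patient in the unexposed group.
- *CCI is cut off in the same three-year way.* The plan takes CCI at BPD diagnosis and gives it no three-year look-back. A three-year residence rule would not equalise CCI history.

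**Conclusion.** The asymmetry is real, and nothing elsewhere in the plan corrects it. Following the plan as written codes an incompletely observed look-back as absence of disease for recent arrivals. The consequence is probably small: a relative fall in prevalence of about 0.15–1.25%, and a prevalence ratio inflated by about 0.5–0.8% in the unequal-share example. With equal shares the contrast is almost unaffected. These figures rest wholly on the assumed shares, even arrival over three years, w of 0.3–0.5 and equal true rates. The documents support none of these values, so the figures are illustrations and not estimates. The larger odds-ratio shifts need a marked imbalance between patients and controls that nothing in the documents indicates. This is a worthwhile refinement and does not threaten the main conclusions.

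**What to change.** Add one criterion to all three studies: continuous residence in Denmark, from civil registration migration data, for the three years before the index date. In Study 1, apply it to controls at the matched patient's index date and before the 1:5 match is fixed, so that a control who fails it is replaced. Report the number excluded, separately for patients and controls.

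If the investigators prefer to keep recent arrivals in the main analysis, pre-specify the same restriction as a sensitivity analysis in each study and report the numbers.

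The cost is one sentence and a filter on a source the plan already draws on. The downside is that restricted results do not represent recent immigrants, which should be stated as a limit on generalisation. The rule is easiest to apply before the match is drawn.
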